7.1. Disposition of Subjects and Withdrawals

Disposition will include tabulations of the number of subjects randomized into each treatment group, the number of subjects completing Day 90 of the study, the number of subjects withdrawing early from the Double-blind Period, tabulated reasons for withdrawal from the Double-blind Period, and number of subjects in each analysis population. This analysis will be conducted on the ITT population.

Additionally, the number of subjects entering the OLE, completing the study through OLE follow up (Day 194), withdrawing early from the OLE, and tabulated reasons for withdrawal from the OLE will be presented for the OLE ITT population.

If a subject discontinues due to COVID-19, those reasons will also be presented.

7.2. Protocol Violations and Deviations

Major protocol violations, including those due to the impact of COVID-19, as determined by a Sponsor blinded review of the data prior to database lock and unblinding of the study, may result in the removal of a subject's data from the PP population.

All protocol violations will be presented in a data listing, with a flag to indicate if a violation was considered major and resulted in the exclusion of the subject from the PP population.

7.3. Demographics and Other Baseline Characteristics

Summary statistics for age, gender, race, ethnicity, height, weight, BMI, and baseline IGA score will be presented by treatment group. See Section 6.1.1 for definition of baseline.

These analyses will be conducted for the ITT and OLE ITT populations.

The number and percent of subjects reporting various medical histories, grouped by MedDRA system organ class (SOC) and preferred term (PT), will be tabulated by treatment group. This analysis will be conducted for the Safety population.

Prior medications will be summarized by treatment group, by the number and percentage of subjects taking each medication, classified using WHO-DDE ATC Class Level 4 and preferred term (ATC Class Level 5) and will be presented by treatment group and overall. This analysis will be conducted for the Safety population. Prior medications are defined in Section 9.7.

7.4. Exposure and Compliance

Compliance by tube weight and compliance by number of doses will be summarized by treatment group using descriptive statistics. The total weight of tubes dispensed and returned, as well as total number of tubes dispensed, returned, and returned unused will also be summarized. This analysis will be conducted for the Safety population and for the OLE Safety population.

A subject is compliant with study product if he or she takes at least 80%-120% of the scheduled doses as assessed by number of doses taken reported, supplemented by tube weight and diary entries. The number and percentage of subjects who were compliant will be tabulated by treatment group for the Double-blind Period and overall for the OLE. Derivations of compliance are defined in Section 6.1.7.

All initial study drug application, drug accountability (dispensed and returned), and subject diary data collected will be listed. Changes in treatment administration or treatment dispensation due to COVID-19 including start and end dates of change, method of alternative administration/dispensation, dosing interruptions, and relevant changes to compliance expectations (weights or tube counts) will be documented from the COVID-19 visit impact log.

8. Efficacy Analysis

All efficacy endpoints will be summarized using the ITT population. The primary analysis will be repeated in the mITT and PP populations.

Summaries of efficacy variables in the OLE will be provided using the OLE ITT. Primary IGA summaries will also be provided for the OLE mITT and OLE PP populations. For continuous efficacy analyses using MMRM, only formal comparisons of change from baseline will be performed in the OLE. No other formal inferential analyses will be conducted for efficacy variables in the OLE.

All efficacy data, regardless of population, will be presented in data listings.

If alternative methods are used for capturing efficacy assessments (i.e., in person not on site at the subject's home, remotely with visual aid, or remotely via telephone), additional sensitivity or subgroup analyses may be performed to assess the potential impact to efficacy analyses. These will be delineated as ad hoc analyses in the CSR.

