- d. Although it is preferable to conduct all necessary study assessments in person (onsite visits), this may not be possible as a result of COVID-19-related travel restrictions. To ensure the safety of subjects, investigators, and site staff, Visits 3-6 and unscheduled visits may be conducted remotely. Screening and baseline visits must be performed onsite only, and must be postponed or scheduled for when onsite visits can be safely conducted.
- e. Limited physical examination to include HEENT, cardiorespiratory, abdomen, range of motion.
- f. IGA: 0 = clear; 1 = almost clear; 2 = mild; 3 = moderate; 4 = severe.
- g. VIIS scale for each body area: chest/abdomen, back, legs, and arms, for a possible overall score = 16.
- h. Roughness (0-4 scale);
- i. Palm/sole fissuring assessment: present/absent/number/pain (0-3 scale).
- j. Photography will be performed at sites with the capability for subjects who sign a photographic ICF. A central reader who will not be an investigator in the study will review the photographs to assess consistency of investigator scoring of LI severity as a quality check.
- k. ECG to be conducted at Screening, Baseline, Day 30, and Day 90 for all subjects. Subjects in the PK substudy will also have postdose ECGs at each serial blood draw on Day 1 and Day 30.
- l. Subjects must be fasting (i.e., at least 8 hours) for clinical laboratory tests, but not for PK blood draws.
- m. Note: Subjects who are premenstrual at Screening but begin menses during the course of the study should follow the pregnancy testing schedule for WOCBP correlating to the visit menses began.
- n. Samples for PK will be drawn from all subjects at Baseline and at each clinic visit. At selected sites among subjects who consent to participate in the PK substudy, samples will be taken predose and at 1, 2, 4, 8, 12, and 24 hours postdose on Day 1. On Day 30, IP will be applied in the clinic for PK substudy subjects, and PK samples will be taken predose and at 1, 2, 4, 8, 12, and 24 hours postdose. Trough levels will be drawn when the subjects are in the clinic for other study visits (i.e., Day 14, Day 60, and Day 90). Visits for PK must occur at least 24 hours after the last application of the IP to avoid contamination of the blood samples with any IP that may have remained in the skin after the last application.

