- o. Study staff will apply initial dose of study drug in the clinic after Baseline measurements, and the amount of study drug used will be measured (i.e., 36-g tube will be measured before and after application to determine amount used).
- p. Study drug provided in 50-g tubes (maximum single application is 36 g). Measure study drug kits (tubes and box, but not leaflets) before dispensing; subjects must record days/times of study drug application in the diaries and any areas of skin not treated, e.g., due to local reactions. Dispense enough additional study drug until next visit (except at Day 90, unless subject consents to continue into OLE).

- q. Confirm study drug compliance by weighing the studykits (tubes and boxes, but not leaflets) and reviewing diary.

Table 2: Schedule of Events for Open-label Extension

	Open-label Treatment Period ^a						Follow-up
	Telephone Visit (Day 97) ^a	Day 104 ± 5 days	Day 120 ± 7 days	Telephone Visit (Day 134)	Day 150 ± 7 days	Day 180 ± 7 days/ET	Day 194 or 14 days after End of Open-label Treatment
Visit		7 ^a	8 ^a		9 ^a	10 ^a	11 ^a
Informed consent ^b							
Physical examination ^c						X	X
Vital signs (blood pressure and pulse)			X	X	X	X	X
Record IGA ^d		X	X		X	X	X
VIIS ^e assessment		X	X		X	X	X
Roughness assessment ^f		X	X		X	X	X
Palm/sole assessment		X	X		X	X	X
Palm/sole fissuring assessment		X	X		X	X	X
Ectropion score		X	X		X	X	X
Clinical laboratory tests (hematology, chemistry, urinalysis) ^g			X			X	
Pregnancy test for female subjects (urine) ^h			X		X	X	X
Coagulation panel			X			X	
12-lead ECG			X			X	
PK blood sample collection ⁱ			X			X	
Application instructions, advice on emollient and sunscreen use ^j	X	X	X	X			
Dispense study drug and diaries ^k		X	X		X		
Concomitant medications	X	X	X	X	X	X	X

	Open-label Treatment Period ^a						Follow-up
	Telephone Visit (Day 97) ^a	Day 104 ± 5 days	Day 120 ± 7 days	Telephone Visit (Day 134)	Day 150 ± 7 days	Day 180 ± 7 days/ET	Day 194 or 14 days after End of Open-label Treatment
Visit		7^a	8^a		9^a	10^a	11^a
Tolerability assessment		X	X		X	X	
Adverse events (and review diaries)	X	X	X	X	X	X	X
Collect all used/unused study drug ¹		X	X		X	X	

Abbreviations: ECG = electrocardiogram; ET = early termination; HEENT = head, eyes, ears, nose, throat; ICF = informed consent form; IGA = Investigator's Global Assessment; PK = pharmacokinetic; OLE = open-label extension; VIIS = Visual Index for Ichthyosis Severity; WOCBP = women of childbearing potential

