6.1.7. Derived Variables

- IGA average score = in protocol version 1.0, IGA was assessed by body area (chest/abdomen, back, arms, and legs). Under protocol version 2.0, this was changed to a global (overall) assessment. For comparability, the average of the body area IGA results will be taken to yield one score for subjects enrolled under protocol version 1.0. Scores will range from 0 to 4. Higher scores indicate worse disease.
- VIIS total score = sum of the individual body area scaling scores, with a range of 0 to 16. Each individual item is scored on a scale of 0-4, where 0 = normal skin; no perceptible scale or smoothening and 4 = confluent, primarily large, thick scales. Higher scores indicate worse scaling.
- Ectropion total score = sum of the 8 individual item scores (lateral apposition, medial apposition, scleral show, conjunctival show, excess tear film, redness of the eye, round canthus, punctum lacrimale), with a range of 0 to 8. Each individual item is scored 0

(nonaffected/no/invisible), 0.5 (≤ 1 mm/emerging), or 1 (affected/yes/visible). Higher scores indicates worse ectropion.

- DLQI total score = sum of the 10 individual item scores, with a range of 0 to 30. Higher scores indicate poorer quality of life.
- CDLQI total score = sum of the 10 individual item scores, with a range of 0 to 30. Higher scores indicate poorer quality of life.
- Number of doses taken = total number of tubes returned – total number of tubes returned unused
- Number of weeks on study = (last day on study – treatment start date + 1) / 7
- Number of expected doses = 2 * number of weeks on study
- Total weight used = total weight of tubes dispensed (grams) – total weight of tubes returned (grams)
- Initial application amount used = tube weight before drug application (grams) – tube weight after drug application (grams), as collected on the initial study drug application CRF
- Compliance by tube weight = total weight used / total weight of tubes dispensed * 100%
- Compliance by number of doses = number of doses taken / number of expected doses * 100%
- Change from baseline = value at current time point – value at baseline.
- TEAE = An AE is defined as treatment emergent if the onset or worsening is at the time of or following the start of the first application of study drug (trifarotene or vehicle) through the Follow-up Visit or Early Termination Visit, whichever occurs first..

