Min, Max	XX, XX	XX, XX	XX, XX	XX, XX

Abbreviation: OLE = open label extension. SD = standard deviation.

Note: Subjects are summarized by actual treatment group. Subjects were randomized to either Trifarotene cream HE1 100 ug/g, Trifarotene cream HE1 200 ug/g, or vehicle in the Double-blind period. All subjects received Trifarotene cream HE1 200 ug/g in the OLE.

SOURCE: Listings 16.2.5.1, 16.2.5.2, 16.2.5.3

Programming note: Continue for Day 30, Day 60, and Day 90.

Table 14.1.5.2
Summary of Drug Accountability (Drug Returned and Dispensed)
OLE Safety Population

Same shell as Table 14.1.5.1

Programming note: Only include one column for Trifarotene cream HE1 200 ug/g.

Continue for Day 104, Day 120, Day 150 and Day 180.

Update Note: to read "Note: Subjects are summarized by treatment group. All subjects received Trifarotene cream HE1 200 ug/g in the OLE."

Table 14.1.5.3
Summary of Treatment Exposure and Compliance
Safety Population

Variable Statistic or Category	Trifarotene cream HE1 100 ug/g (N=XX)	Trifarotene cream HE1 200 ug/g (N=XX)	Vehicle (N=XX)	Overall (N=XX)
Compliance by Tube Weight (%) [1]				
n	XX	XX	XX	XX
Mean (SD)	XX.X (XX.XX)	XX.X (XX.XX)	XX.X (XX.XX)	XX.X (XX.XX)
Median	XX.X	XX.X	XX.X	XX.X
Min, Max	XX, XX	XX, XX	XX, XX	XX, XX
Compliant	XX (XX.X%)	XX (XX.X%)	XX (XX.X%)	XX (XX.X%)
Not Compliant	XX (XX.X%)	XX (XX.X%)	XX (XX.X%)	XX (XX.X%)
Compliance by Number of Doses (%) [2]				
n	XX	XX	XX	XX
Mean (SD)	XX.X (XX.XX)	XX.X (XX.XX)	XX.X (XX.XX)	XX.X (XX.XX)
Median	XX.X	XX.X	XX.X	XX.X
Min, Max	XX, XX	XX, XX	XX, XX	XX, XX
Compliant	XX (XX.X%)	XX (XX.X%)	XX (XX.X%)	XX (XX.X%)
Not Compliant	XX (XX.X%)	XX (XX.X%)	XX (XX.X%)	XX (XX.X%)

Abbreviation: SD = standard deviation.

Note: Percentages are n/Number of subjects in the Safety population within actual treatment group and overall*100. A subject is compliant with study product if he or she takes at least 80%-120% of the scheduled doses as assessed by diary entries, supplemented by tube weight.

[1] Compliance by tube weight = total weight used / total weight of tubes dispensed *100%, where total weight used = total weight of tubes dispensed (grams) – total weight of tubes returned (grams)

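### The SAP names two governing sources for the 80%-120% compliance rule without an order of precedence, and its dose formula scores an unreturned used tube as a dose not taken

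*SAP*

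**What the plan says.** Section 7.4 sets the compliance band at 80%-120% of scheduled doses, "as assessed by number of doses taken reported, supplemented by tube weight and diary entries". It then points elsewhere for the calculation: "Derivations of compliance are defined in Section 6.1.7". Section 6.1.7 gives "Number of doses taken = total number of tubes returned – total number of tubes returned unused" and "Number of expected doses = 2 * number of weeks on study", with weeks on study running from the treatment start date to the last day on study, both days included.

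The note to the shell of Table 14.1.5.3 applies the same band "as assessed by diary entries, supplemented by tube weight". The table cites the diary listing among its sources, but its two compliant/not-compliant blocks are by tube weight and by number of doses, and both are defined from tubes. Footnote [2] of that table gives yet another dose count: dispensed minus returned minus returned unused.

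On collection, Table 1 in Section 3.7 schedules return of used and unused drug at Days 14, 30, 60 and 90. Note d says that "Visits 3-6 and unscheduled visits may be conducted remotely"; Visit 6 is Day 90. Note p says that "subjects must record days/times of study drug application in the diaries".

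Section 5 makes compliance a condition of the PP and OLE PP populations. Section 8 repeats the primary analysis in PP and summarises IGA in OLE PP.

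**The concern.** There are two linked faults. First, the diary is a supplement in Section 7.4 and the governing source in the table note, and nothing says which prevails when they disagree. Second, the count that Section 7.4 relies on does not measure doses applied. It measures used tubes that came back. Each application uses a new tube (Section 3.4), so a used tube left at home reduces the count exactly as a skipped application would.

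The SAP has no rule for unreturned tubes. Section 7.4 says that COVID-19 changes to expected weights or tube counts will be documented from the visit impact log, but no formula uses them. At stake are the tabulated compliance rate and, through it, who is eligible for the PP sensitivity analysis.

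**Working it through.** The SAP states no compliance figure to reproduce, so the check applies its own formulas.

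**Inputs from the SAP.** Expected doses = 2 × days/7 (6.1.7). Lower limit 80% (7.4). One tube per application (3.4). Day 90 window 83 to 97 (Table 3).

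**Assumed inputs.** The subject applies all 26 doses over 90 days. For footnote [2] only, 28 tubes are dispensed and 2 are returned unused.

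**Threshold at Day 90.** Expected = 2 × 90/7 = 25.71. The limit is 0.80 × 25.71 = 20.57, so at least 21 used tubes must come back. Each missing tube costs 1/25.71 = 3.9 percentage points.

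**Score by Section 6.1.7:**

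| Used tubes not returned | Doses counted | Compliance |
|---|---|---|
| 0 | 26 | 101.1% |
| 1 | 25 | 97.2% |
| 5 | 21 | 81.7% |
| 6 | 20 | 77.8% |
| 8 | 18 | 70.0% |
| 9 | 17 | 66.1% |

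A complete diary would give 26/25.71 = 101.1% in every row.

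**What one uncollected interval does.** Day 60 to 90 is 30 days: 2 × 30/7 = 8.6 tubes, so 8 or 9, which is enough to cross the limit. Day 30 to 60 is the same length. Day 14 to 30 is 16 days: 2 × 16/7 = 4.6 tubes, so at most 5, which leaves 81.7% and the subject still compliant. Loss of one interval therefore matters for the two long intervals, and only if the tubes are not handed in at a later visit.

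**Sensitivity to the inputs.** At Day 83, expected doses are 23.71 and 19 tubes are needed. At Day 97, expected doses are 27.71 and 23 tubes are needed. Over that window, with 24 to 27 doses applied, the tipping point ranges from 2 missing tubes (24 applied, Day 97) to 9 (27 applied, Day 83).

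**Footnote [2] of Table 14.1.5.3.** If everything is returned: 28 − 28 − 2 = −2 doses (−7.8%). If no used tube is returned: 28 − 2 − 2 = 24 doses (93.3%). It runs in the opposite direction to 6.1.7 and cannot settle the question.

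**Weight of one subject.** With 65 enrolled and arms assumed equal, 65/3 = 21.7 per arm, so one subject is 1/21.7 = 4.6% of an arm. This is the weight of one misclassification. It says nothing about how many there are.

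**The case against.** Five points can be made on the other side, and most of them limit the consequence.

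- **The diary is not immune.** A reader might infer that a diary-based rule would avoid the problem. Listing 16.2.5.3 has a field for whether diary data were collected at the visit, and a note for when they were not. A remote visit can lose the diary as well as the tubes. This stands.
- **The table note is not a second working rule.** A reader might infer that adherent subjects stay in PP under the note and leave under Section 7.4, so that PP turns on which sentence is programmed. Neither Table 14.1.5.3 nor Section 6.1.7 contains a diary-derived count, so this is not shown. The contradiction in wording remains.
- **Exclusion from PP is not mechanical.** Section 7.4 lets weight and diary supplement the count. Section 5 has COVID-19 deviations evaluated for PP eligibility before lock, and Section 7.2 adds a blinded sponsor review under which major violations may lead to removal. This stands, but none of these passages says when or how the tube count is overridden.
- **The trigger may be rare.** Collection is scheduled at every clinic visit. Permission for a remote visit does not mean that tubes are never returned, and a few lost tubes usually change nothing. The document gives no frequency in either direction.
- **The primary result is safe.** Efficacy is primarily analysed in ITT, and the PP repeat is labelled a sensitivity analysis. This stands.

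**Conclusion.** The inconsistency is real and the dose formula is wrong for unreturned tubes. Under Section 6.1.7 a subject with 26 applications by Day 90 is labelled non-compliant once six used tubes are missing (77.8%), although every dose was applied. That figure rests on the assumed 26 applications; across the Day 90 window the tipping point is 2 to 9 tubes.

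The reach is the compliance tables and the PP and OLE PP analyses. For OLE PP, compliance must hold from baseline through end of treatment, and Visits 7-11 may also be remote. The documents do not show that adherent subjects would automatically leave PP, or that many would be affected. They show that status would then rest on a pre-lock judgement with no stated rule. The point should be corrected, but it does not threaten the primary conclusion.

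**What to change.** Before populations are assigned:

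1. Name one governing dose-count variable in Section 6.1.7. Use it identically in Section 7.4, the Table 14.1.5.3 note and footnote [2], and the PP and OLE PP compliance criterion.
2. State that an unreturned tube is not scored as a missed dose. For any interval with incomplete tube return, use the diary-recorded applications (Listing 16.2.5.3), taking care that the Day 1 clinic application (Listing 16.2.5.1) is counted once. Where the diary is missing, use the tube count.
3. Say what happens when an interval has neither a diary nor a complete tube return. Otherwise the fallback again scores those doses as missed.
4. State the order of precedence. Either the diary or the tube count may be primary; the documents do not require one over the other.

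The cost is wording in a few places and one derivation, using data already collected. The small downside is some reliance on self-report, which can be limited by keeping tube counts as a cross-check.

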8.1. Primary Efficacy Analysis

8.1.1. Investigator's Global Assessment (IGA)

The 5-point IGA is a measure of disease severity and meets the need for a clinically meaningful measure of success for ichthyosis studies. Each level of severity will consider both the severity of scaling and the severity of roughness. The investigator will rate the subject's condition using the 5-point scale (0-4), excluding the following areas: knees, elbows, neck, palms, soles, axillae, groin, and scalp, where higher scores represent more severe disease. The IGA is collected at all clinic visits. The scoring is as follows below in Table 4.

Table 4: IGA Scoring Definitions

Score	Definition
0	Clear: No scaling and no roughness
1	Almost clear: Occasional fine scales; hardly palpable roughness (mostly smooth)
2	Mild: Small and fine scales predominate; no more than a few large scales; mild roughness on palpation
3	Moderate: Some large scales that may be thick; coarse roughness on palpation
4	Severe: Confluent, primarily large (>1cm) thick scales with plate-like hyperkeratosis

The primary efficacy endpoint is the proportion of subjects in each treatment group who experience successful resolution of LI where “success” is defined as clear/almost clear overall and at least a 2-grade change from Baseline at Day 90/EOT in the Double-blind Period on the 5-point IGA scale. The number and percentage of subjects with treatment success will be summarized by treatment group. The primary efficacy endpoint will be analyzed using a logistic regression model with treatment, baseline IGA score, and age group as factors. The odds ratios and 95% CIs for the odds ratios will be presented. The difference in proportions between the active trifarotene cream HE1 groups and vehicle cream group, 95% CIs for the differences, and *P* values for the differences in treatment will also be presented.

The potential for heterogeneity of treatment effects will be assessed by testing treatment-by-factor interactions. The logistic regression model for the primary analyses will be expanded to include the treatment-by-age group interaction. In the event of quasi or complete separation, the logistic regression model will use Firth’s penalized maximum likelihood estimation.

The same logistic regression model will be used to analyze the proportion of subjects with at least a 50% reduction in IGA score from baseline as a secondary analysis.

The change from baseline IGA score will be analyzed using a mixed model for repeated measures (MMRM). The MMRM model will include change from baseline in IGA score as the dependent variable, treatment, study visit, treatment-by-visit interaction, and age group as fixed effects, subject as a random effect, and baseline IGA score as a covariate. All post-baseline study visits will be included in the model; however, the primary comparison will be between the active trifarotene cream HE1 groups and vehicle at Day 90. An unstructured covariance matrix will be used to model the within-subject errors. The Kenward-Roger approximation will be used to estimate degrees of freedom. In case of convergence issues, other covariance structures will be explored including autoregressive (AR(1)), compound symmetry (CS), and variance components (VC) with each model fit to find the covariance structure with the best fit. The fit statistics will be compared for all covariance structures; the structure with the smallest Akaike information criterion will be retained as the preferred model and noted in the resulting table. For the OLE period, the model will not include treatment or treatment-by-visit interaction since all subjects receive the same treatment in the OLE.

The least squares (LS) mean change from baseline will be presented along with the associated 95% CI within each treatment group. The overall *P* value of the model will be presented to test

the null hypothesis that the change from baseline to subsequent study visit is 0 with a 2-sided alternative considering a difference in either direction.

In comparing treatments (active trifarotene cream HE1 groups minus vehicle), LS mean differences in change from baseline will be presented along with associated 95% CIs and *P* values. The null hypothesis that the difference in change from baseline in active trifarotene cream HE1 groups minus control vehicle is 0 with a 2-sided alternative considering a difference in either direction. Even if a difference from vehicle is observed, as described above, successful treatment is defined as clear/almost clear overall (IGA scores of 0 or 1) and at least a 2-grade change from baseline.

The observed value and change from baseline in IGA score will also be summarized descriptively by study visit and treatment group using descriptive statistics in addition to the above noted models for the Double-blind Period and OLE. Categorical IGA scores will also be presented.

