6.1.2. Adjustments for Covariates

If there is a statistical difference among treatment groups with respect to baseline characteristics, that variable may be added to the statistical models as a blocking factor or covariate to determine the effect on treatment. Age group and baseline score are planned for inclusion in statistical models, unless otherwise indicated. Age group will be categorized as adolescents (ages 12 to 17 years, inclusive) and adults (≥ 18 years).

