[3] Estimates for odds ratio, 95% CI for odds ratio, and P value are from a logistic regression model with treatment, baseline IGA score, and age group as factors. The odds ratio is the estimate of the odds of having successful resolution of LI for subjects treated with Trifarotene cream HE1 relative to that for subjects treated with vehicle. Age group is defined as adolescents (ages 12 to 17 years, inclusive) and adults ≥18 years.

SOURCE: Listing 16.2.6.1

Programming note: If Firth's penalized maximum likelihood is used, add 'Firth's penalized maximum likelihood estimation is used.' to end of 'Note:' footnote. If the treatment-by-age interaction is significant, include it in the logistic regression model and update footnote [3] to include this factor. After Day 90, repeat table for Days 14, 30, and 60.

Table 14.2.1.1.2
Proportion of Subjects with Successful Resolution of LI in the OLE
OLE ITT Population

Study Visit Statistic	Trifarotene cream HE1 200 ug/g (N = XX)
Day 104 n [1] Successful Resolution [2]	XX XX (XX.X%)
Day 120 n [1] Successful Resolution [2]	XX XX (XX.X%)
Day 150 n [1] Successful Resolution [2]	XX XX (XX.X%)
Day 180 n [1] Successful Resolution [2]	XX XX (XX.X%)
Day 194 n [1] Successful Resolution [2]	XX XX (XX.X%)

Abbreviation: CI = confidence interval; EOT = end of treatment; IGA = Investigator's Global Assessment; ITT = intent to treat; LI = Lamellar Ichthyosis; OLE = open label extension.
Note: Percentages are n/Number of subjects in the OLE ITT population within treatment group*100. All subjects received Trifarotene cream HE1 200 ug/g in the OLE. The 5-point (0 - 4) IGA is a measure of disease severity which considers both scaling and roughness. Higher IGA scores represent more severe disease.

[1] Number of subjects with an IGA assessment at each visit.

[2] Number of subjects with successful resolution of LI at a visit. Successful resolution is defined as clear/almost clear overall (IGA of 0 or 1, respectively) and at least a 2-grade change from Baseline on the 5-point (0 - 4) IGA scale. Baseline is defined as the last non-missing assessment recorded prior to the first dose of treatment in the Double-blind Period.

SOURCE: Listing 16.2.6.1

Table 14.2.1.2.1
Primary Analysis, Sensitivity: Logistic Regression Analysis of Successful Resolution of LI
mITT Population

Same shell as Table 14.2.1.1.1

Programming note: Update Abbreviations to remove ITT and include mITT = modified intent-to-treat.

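### The primary logistic model calls baseline IGA a factor although version 1.0 subjects carry averages in 0.25 steps; read literally, sparse baseline levels would often trigger the Firth fallback, so the coding and the Firth inference should be stated

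*SAP*

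**What the plan says.** Section 8.1.1 defines the primary analysis: "The primary efficacy endpoint will be analyzed using a logistic regression model with treatment, baseline IGA score, and age group as factors". Footnote [3] of the primary table shell (Table 14.2.1.1.1) repeats it: "logistic regression model with treatment, baseline IGA score, and age group as factors". No coding or CLASS statement is given for this model.

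For the MMRM of the same score, the same section has "subject as a random effect, and baseline IGA score as a covariate". Section 6.1.2 also names the two roles as alternatives, saying of a baseline variable that differs between arms "that variable may be added to the statistical models as a blocking factor or covariate".

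Section 6.1.7 explains that protocol version 1.0 graded IGA separately in four body areas and later versions graded it once overall. To make them comparable, "the average of the body area IGA results will be taken to yield one score for subjects enrolled under protocol version 1.0". There is no rounding rule.

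Section 8.1.1 also sets a fallback: "In the event of quasi or complete separation, the logistic regression model will use" Firth's penalised likelihood. It does not say whether the Firth fit is reported with Wald or profile-likelihood inference.

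**The concern.** Treatment and age group are plainly class variables, and baseline IGA stands in the same list. A programmer who follows the sentence puts it in the CLASS statement. Subjects graded overall enter with 3 or 4. Version 1.0 subjects can also enter with 3.25, 3.5 or 3.75, and each of those values becomes its own level holding one or a few people.

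A level whose members all succeed or all fail has no finite maximum-likelihood estimate. Under the plan's rule the whole primary model then changes estimator, although the treatment effect itself is estimable. The baseline average of one or two version 1.0 subjects could decide how the primary odds ratio is computed. The answer could also differ between the ITT, mITT and PP runs, between visits and between imputed datasets. With 65 subjects enrolled of 120 planned, there is little power to spare.

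**Working it through.** **Inputs from the SAP.** 65 subjects enrolled (Section 1), so 65/3 = 21.7, about 22 per arm. Success 70% on active and 40% on vehicle (Section 3). Two-sided 0.05 (Section 4.1). Eligible baseline IGA 3 to 4 (Section 3.1). Mean of four integer grades, hence steps of 1/4 = 0.25 (Section 6.1.7).

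**Assumptions not in the SAP.** 5 to 25 version 1.0 subjects, all adults, with averages spread evenly over 3, 3.25, 3.5, 3.75 and 4. Other subjects at 3 or 4 with equal chance, 20% of them adolescents. Baseline log-odds slope 0 to -1 per grade. No missing data.

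**The plan's own figure.** The SAP gives no power for the logistic model. For a two-sided Fisher test with 32 per arm it claims more than 80%. Exact enumeration gives 0.619, and 0.397 at 22 per arm. That discrepancy is a separate matter; it only shows how little power there is to lose.

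**Step 1: when a level separates.** With k subjects in a level and average success p = (0.4 + 0.7 + 0.7)/3 = 0.6, the chance of a single outcome is p^k + (1-p)^k:

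- k = 1: 1
- k = 2: 0.36 + 0.16 = 0.52
- k = 3: 0.216 + 0.064 = 0.28

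For three fractional levels of equal size, the chance that at least one separates is 1 - (1-0.52)^3 = 0.89 at k = 2 and 1 - (1-0.28)^3 = 0.63 at k = 3. A singleton always separates. Uneven level sizes raise the chance.

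**Step 2: simulation at 22 per arm, 200 µg/g v vehicle, 1,500 to 2,000 trials per setting.** Both codings were fitted to the same simulated data. Paired entries are for slopes 0 and -1.

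| Version 1.0 subjects | Separation, linear | Separation, class | Power, linear | Power, class with Firth Wald | Power, class with ordinary ML |
|---|---|---|---|---|---|
| 0 | 0.005 / 0.007 | 0.005 / 0.007 | 0.506 / 0.503 | 0.506 / 0.503 | 0.506 / 0.504 |
| 5 | 0.006 / 0.009 | 0.903 / 0.889 | 0.505 / 0.493 | 0.427 / 0.439 | 0.479 / 0.495 |
| 10 | 0.007 / 0.007 | 0.875 / 0.880 | 0.541 / 0.480 | 0.449 / 0.412 | 0.515 / 0.476 |
| 15 | 0.015 / 0.016 | 0.778 / 0.762 | 0.517 / 0.499 | 0.437 / 0.441 | 0.503 / 0.489 |
| 25 | 0.035 / 0.031 | 0.437 / 0.454 | 0.505 / 0.479 | 0.462 / 0.457 | 0.494 / 0.490 |

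The loss from linear to class with Firth Wald runs from 0.479 - 0.457 = 0.022 to 0.541 - 0.449 = 0.092. At 32 per arm it is about 2.5 to 5 points.

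**Step 3: where the loss comes from (slope -0.5).**

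| Per arm, version 1.0 subjects | Linear, ML Wald | Linear, Firth Wald | Class, fallback Wald | Class, fallback profile | Class, ML Wald |
|---|---|---|---|---|---|
| 22, 5 | 0.512 | 0.450 | 0.444 | 0.488 | 0.498 |
| 22, 15 | 0.525 | 0.465 | 0.460 | 0.510 | 0.520 |
| 32, 15 | 0.686 | 0.641 | 0.626 | 0.658 | 0.667 |

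The linear model loses almost as much when Firth Wald is forced on it (0.512 to 0.450), so the Wald test drives most of the loss. Sparse levels under ordinary ML cost about 0 to 3 points. With profile likelihood the loss is 0.512 - 0.488 = 0.024, 0.525 - 0.510 = 0.015 and 0.686 - 0.658 = 0.028.

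**Step 4: null runs (40% in every arm, 22 per arm).** Class coding with fallback rejected in 3.5% to 3.8% of trials with Wald and 4.4% with profile likelihood. The linear term rejected in 4.2% to 4.3%.

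**Step 5: other assumptions.** With averages drawn as 3 + Binomial(4, 0.5)/4 and 4, 8 or 15 version 1.0 subjects, separation was about 89%, 85% and 56%. Power was about 41%, 41% and 45%, against 47% to 50% linear. With a less mixed baseline, Binomial(4, 0.2), separation was 65% to 75% and power 43% to 45%, against 49% to 50%. In null runs under the binomial draw the linear term rejected in 4.8% to 5.5% of trials against 3.6% to 4.4%, so part of the power gap there reflects a less conservative test.

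**The case against.** The best reply is that *factors* is loose wording and nobody intends class coding. Several places support this:

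- Section 6.1.2, on covariate adjustment, groups age group and baseline score as planned model terms.
- The footnote of the MMRM shell (Table 14.2.1.6.1) calls baseline IGA a fixed-effect term, although Section 8.1.1 calls it a covariate.
- Section 8.1.1 promises treatment-by-factor interactions but adds only the one with age group.
- In the imputation code of Section 8.1.2, only treatment appears in a CLASS statement.
- The same sentence is reused for roughness and palm/sole.

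This stands in part. A reader might infer that the plan definitely fits baseline IGA as a class variable; the text does not settle that. It does leave the scale of a primary-model term open, and two programmers could report different primary odds ratios.

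A reader might also infer that the sparse levels themselves drain power. They mostly do not: the larger part is Firth's Wald test, which the SAP never names. Nor is the analysis shown to be invalid. The fallback is prespecified, its trigger is mechanical, and simulated type I error stays below 5%.

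Finally, a rounding rule in Section 6.1.7 would remove the extra levels. That is true, but it would also change how the outcome is graded, which is a separate decision.

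**Conclusion.** The concern holds in a limited, conditional form. The SAP does not fix how baseline IGA enters its primary model, and the literal reading combines badly with unrounded averages. Under that reading, and if version 1.0 subjects had unequal area grades, the switch to Firth becomes common: roughly 45% to 90% of simulated trials, against about 1% to 3% with a linear term. The price is about 2 to 9 points of power with Firth Wald tests and about 1.5 to 3 with profile likelihood.

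These sizes rest on an assumed number and spread of version 1.0 averages, neither of which is in the SAP. If every average is 3 or 4, the problem vanishes. Type I error is not inflated. The matter deserves correction because the estimator of the primary odds ratio should not hang on a few baseline values, and the correction is nearly free.

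**What to change.** In Section 8.1.1, footnote [3] of Table 14.2.1.1.1 and the tables that reuse that shell (mITT, PP, multiple imputation, 50% IGA reduction):

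- Enter baseline IGA as a single continuous covariate, as the MMRM does.
- Keep treatment and age group as class factors.
- If separation still triggers Firth, report profile penalised-likelihood confidence intervals and P values for the odds ratios.

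This takes a sentence or two and a footnote, and Section 1 places filing of the plan before any unblinded analysis. The price is an assumed linear baseline effect on the log-odds over a one-grade range.
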